## Design & Procedures

The study design reflects our objective of identifying the mechanisms responsible for the increased risk of CVD among patients with hypertension and insomnia, and to determine if these mechanisms can be favorably altered by improving sleep quality. We propose to utilize a behavioral intervention to manipulate sleep quality in 150 adults with hypertension and comorbid insomnia. This mechanistic clinical trial design will assign all 150 participants to a 6-week CBT-I intervention, which has been shown to markedly improve sleep quality and promote consolidated sleep in approximately 60% of those treated; whereas approximately 40% do not respond to CBT-I. While CBT-I is generally effective, the anticipated wide-ranging treatment response will provide the prerequisite variability in sleep quality changes that will afford us the opportunity to help identify the mechanisms by which insomnia conveys CVD risk and by which improved sleep may lower CVD risk. Our design (see Figure 5 below) will include a 6-week run-in period, without treatment, to document the stability of sleep quality, ABP, and CVD risk mechanisms, which will serve as a basis of comparison following CBT-I treatment. Assessments will be performed at baseline, after the 6-week run-in period, after the subsequent 6-week CBT-I intervention, and at 6-month follow-up. Importantly, the study design will also establish whether these insomnia-driven CVD risk mechanisms are modifiable by CBT-I for participants who show improved sleep following treatment.

**Screening Assessments.** Initial telephone screening will be used to ascertain whether potential participants are likely to meet the study eligibility criteria, with a focus on previously observed clinic BPs and the presence of insomnia symptoms. For those who are likely eligible, the first of two screening sessions will be scheduled, at which informed consent will be first obtained. A medical history will be taken for eligible participants. For women, menopausal status will be documented by self-reported menstrual bleeding, using the criteria described by Tom and colleagues. Status categories are postmenopausal (natural or surgical), perimenopausal, and premenopausal. Menopausal status will be considered as a potential covariate in analytic models.

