**Sleep Apnea Screening and Exclusion Assessments.** A previous diagnosis of obstructive sleep apnea (OSA) is an exclusion criterion. The Snoring, Tiredness, Observed apnea, high BP, BMI, Age, Neck circumference and male Gender (STOP-BANG) questionnaire will be used to screen potential study participants for OSA. Potential participants scoring  $>3$  on this scale, who otherwise meet all study eligibility criteria, will be required to complete a further screening assessment by the WatchPat device (Itamar Medical, Caesarea, Israel). The WatchPat device is a convenient tool that is worn in the comfort of potential participants' own bedroom and is found to be a sensitive and specific assessment for identifying the presence of OSA. Participants are given the option of using a Duke owned iPhone or their own smart phone that works with the WatchPat device. Potential participants showing an apnea-hypopnea index (AHI)  $> 15$  will be notified that they are no longer eligible to continue, and will be encouraged to seek additional evaluation and treatment through their physician. If someone has completed a polysomnography sleep test in the last 3 months, these results can be used instead of the Watchpat device.

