## Selection of Subjects

**Inclusion Criteria.** Systolic BP  $\geq$  130 mm Hg based upon two standardized BP screening assessments a current diagnosis of insomnia disorder as defined in the International Classification of Sleep Disorders (ICSD-3);84 or undiagnosed, but suspected, insomnia disorder that is confirmed at their screening lab visit; an age range of 30-60 years.

**Exclusion Criteria.** Uncontrolled hypertension (screening office BP > 160/100 mm Hg); antihypertensive medication use; cardiovascular medications; previously diagnosed moderate or severe obstructive sleep apnea; severe obesity defined by BMI > 40 kg/m^2; pacemakers; atrial fibrillation; acute coronary syndrome or coronary revascularization procedure within 6 months of enrollment; congestive heart failure; identifiable cause of hypertension (e.g., primary hyperaldosteronism, renal artery stenosis, untreated hyper- or hypothyroidism, chronic kidney disease, Cushing's disease, pheochromocytoma, coarctation of the aorta); severe uncorrected valvular heart disease; current pregnancy; active diagnosis of psychosis, bipolar disorder, current treatment of PTSD with exposure based therapy; severely impaired hearing or speech; participation in another interventional study to address insomnia; rotating shift workers; diabetes; prominent suicidal or homicidal ideation (as assessed through a clinical interview); psychiatric hospitalization within the past 12 months; unstable comorbid sleep disorder requiring assessment and/or treatment outside of the study protocol; medical or psychiatric conditions judged to be the primary cause of insomnia; alcohol or drug abuse within 12 months; dementia; inability to comply with the assessment procedures or inability to provide informed consent.

**Identification.** The study coordinator and research associate will identify patients using the electronic medical records (Maestro). A detailed description is below in Subject Recruitment. If a participant is interested and their electronic medical record (EMR) is not available, study staff can ask the participant the eligibility criteria that would have been collected in the EMR to collect the medical history necessary to determine eligibility.

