**Analysis Plan:** General linear models will be used to examine the associations between improvements in sleep quality on improvements in BP dipping, controlling for age, gender, race, baseline sleep efficiency, baseline mean 24-hour BP, and pretreatment BP dipping, with post-treatment BP dipping as the criterion. Significance will a priori be set at  $P = .05$ . For follow-up analyses of 6-mo BP dipping, linear repeated measures mixed models will be examined in which 6-wk and 6-mo BP dipping both serve as outcome variables using the same covariates above. As an a priori explanatory analysis for our follow-up analyses, we will examine potential time X sleep efficiency interactions in order to examine the extent to which the association between sleep efficiency and BP dipping at six weeks differs from that at six-months. In addition, we will conduct an area under the curve analysis to examine overall associations that apply to both 6-wk and 6-mo in order to determine whether larger improvements in sleep are associated with larger improvements in BP outcomes in an overall sense. Because other ABP outcomes could plausibly be improved by CBT-I and also will reflect improved nighttime dipping, we will conduct parallel analyses of nighttime average BP and 24-hour BP levels.

**AIM 2:** Evaluate candidate mechanisms of CVD risk related to sleep quality in patients with hypertension and comorbid insomnia

**Hypothesis 2:** Improved sleep quality will be accompanied by: (i) reduced nighttime SNS activity; (ii) enhanced vascular endothelial function; (iii) reduced arterial stiffness, and; (iv) improved lipid profile.

**Analysis Plan:** General linear models will be used to examine the associations between improved sleep efficiency and improvements in mechanisms of CVD risk, controlling for age, gender, race, baseline sleep efficiency, and the pre-treatment (post run-in) level of the outcome. For our analyses of vascular endothelial function only, we also will adjust for baseline arterial diameter, consistent with our prior work. Follow-up analyses will follow the same approach as in Hypothesis 1, using linear repeated measures mixed models with 6-wk and 6-mo levels serving as the outcome variables.

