With respect to participant inclusion/exclusion criteria, we chose to focus on hypertension with comorbid insomnia because of the putative mechanisms of CVD risk, including blunted nighttime BP dipping, heightened sympathetic activity, arterial stiffness, and endothelial dysfunction being evident in this population, and therefore affording the opportunity for their improvement following CBT-I as a manifestation of sleep-related mechanisms of CVD risk. We also adopted the new ACC/AHA guidelines for defining hypertension at lower BP levels, with our selection of systolic BP  $\geq 130$  mm Hg as the inclusion criterion. We also excluded antihypertensive medication use, as different classes of medications have different half-lives and may distort the patient's normal circadian BP profile. Many individuals with recently diagnosed hypertension refuse antihypertensive therapy in favor of attempting lifestyle changes first; for those with comorbid insomnia, enrolling in our proposed study will provide them an opportunity to help control their BP, as well as improve their sleep. We also elected to exclude sleep apnea because of its association with hypertension presenting a potential confounding of our observations. Interestingly, a recent review and meta-analysis failed to find conclusive evidence that continuous positive airway pressure (CPAP) reduced the risk of CVD events in sleep apnea patients. However, in addition to compliance with CPAP therapy being difficult to ascertain, sleep apnea is frequently comorbid with insomnia, and when sleep apnea is diagnosed, comorbid insomnia is rarely treated, further complicating our understanding of sleep apnea and its treatment effect on BP.

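### The Aim 1 and Aim 2 models omit BMI and any apnea measure, although sleep response is not randomised and the protocol names sleep apnea as a potential confounder

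*Combined protocol and SAP*

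**What the plan says.** **Covariates (Combined protocol and SAP, ANALYSIS PLAN).** The six-week Aim 1 model has six covariates: "controlling for age, gender, race, baseline sleep efficiency, baseline mean 24-hour BP, and pretreatment BP dipping". The six-month mixed model keeps that set: "6-wk and 6-mo BP dipping both serve as outcome variables using the same covariates above". The Aim 2 models are fitted "controlling for age, gender, race, baseline sleep efficiency, and the pre-treatment (post run-in) level of the outcome", with one addition: "For our analyses of vascular endothelial function only, we also will adjust for baseline arterial diameter". Elsewhere, under Design & Procedures, one more candidate is named: "Menopausal status will be considered as a potential covariate in analytic models". The mediation section adds none. The list of candidate effect modifiers is open-ended, but it mentions neither BMI nor apnea.

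**Confounding (D.2. METHODOLOGICAL ISSUES).** "We also elected to exclude sleep apnea because of its association with hypertension presenting a potential confounding of our observations".

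**Screening.** Under Design & Procedures the STOP-BANG "questionnaire will be used to screen potential study participants for OSA". Those scoring above 3 go on to the WatchPat device, and an AHI above 15 excludes them. Safety Monitoring gives the same AHI limit, but describes referral to the device as resting on the questionnaire together with the diagnostic sleep interview. Selection of Subjects excludes "severe obesity defined by BMI > 40 kg/m"².

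**The concern.** There is no comparison group. Aims 1 and 2 are answered by the slope of the outcome on each participant's sleep-efficiency change, so the covariate list is the main protection against stable traits that differ between good and poor responders. The run-in deals with transient fluctuation, not with stable traits.

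Restriction handles apnea only in part. AHI up to 15 and BMI up to 40 stay in the sample. If either trait goes with both a weaker sleep response and a worse outcome, part of the estimated slope would reflect the trait and not sleep. The result could then be read as evidence for a sleep mechanism.

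**Working it through.** **1. The plan's own power figure.** Inputs from Power and Sample Size Considerations: N = 150, attrition 15%, alpha 0.05 (taken as two-sided), r = 0.25, power 80%. Analysed n = 150 × 0.85 = 127.5, taken as 127. With k covariates,

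power = Φ(atanh(r) × √(n − k − 3) − 1.96).

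With k = 0: Φ(0.2554 × √124 − 1.96) = Φ(0.884) = 0.812. The stated 80% reproduces.

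**2. How an omitted trait would act on the dipping slope.** The documents give none of the following inputs; they are assumptions.
- The trait correlates c with sleep-efficiency response and c with true dipping, in the same direction.
- Sleep has no effect on dipping.
- One 24-hour record measures usual dipping with reliability R, so pre- and post-treatment dipping correlate R.

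Response then correlates r = c² × √R with dipping at either time. Conditioning on pre-treatment dipping leaves

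partial r = r(1 − R) / √[(1 − R²)(1 − r²)].

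Example, c = 0.3 and R = 0.5: r = 0.09 × 0.7071 = 0.0636. Partial r = 0.0318 / √(0.75 × 0.996) = 0.0368. On the Fisher z scale the shift is 0.0368 × √123 = 0.408. The rejection rate is P(Z > 1.552) + P(Z < −2.368) = 0.060 + 0.009 = 6.9%.

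| c | R | spurious partial r | share of 0.25 | type I error |
|---|---|---|---|---|
| 0.2 | 0.4 | 0.017 | 7% | 5.4% |
| 0.2 | 0.6 | 0.016 | 6% | 5.3% |
| 0.3 | 0.4 | 0.037 | 15% | 7.0% |
| 0.3 | 0.6 | 0.035 | 14% | 6.7% |
| 0.4 | 0.4 | 0.067 | 27% | 11.5% |
| 0.4 | 0.6 | 0.062 | 25% | 10.7% |

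The formula conditions on pre-treatment dipping alone. Age, gender, race, baseline sleep efficiency and baseline 24-hour BP are also in the Aim 1 model and would be expected to absorb part of the trait's effect.

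**3. Cost of adjustment.** Formula of step 1, n = 127, r = 0.25:
- k = 6 (planned Aim 1 model): power 0.7923, r detectable at 80% power 0.2523
- k = 7 (adding BMI): 0.7889, 0.2534
- k = 8 (adding BMI and STOP-BANG): 0.7855, 0.2544

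Two covariates cost 0.7923 − 0.7855 = 0.0068, about 0.7 points of power.

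**The case against.** The strongest reply is that bias needs two links, and the documents support at most one. They tie sleep apnea to hypertension. Nowhere do they say that BMI or mild apnea predicts the response to CBT-I. A reader might also infer that the protocol treats BMI as a confounder. It does not: it says this of sleep apnea only, and only as a possibility. All of this stands, and it is why the point is conditional.

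Restriction is a legitimate form of control. A reader might conclude that people with a STOP-BANG of 3 or less are not screened at all. That goes too far: section C.4 gives a diagnostic sleep interview at screening, and Safety Monitoring makes it part of the route to the device. Undetected apnea remains possible, but the screen is not the questionnaire alone. How much diagnosed mild apnea is admitted is unclear, because Design & Procedures excludes any previous diagnosis and Selection of Subjects only moderate or severe disease. Those passages must be reconciled.

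The reliability range is also assumed. Section C.5 says one successful 24-hour record represents the diurnal profile adequately. That is not a reliability coefficient, but it argues against assuming the low end.

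The dipping figures do not transfer to Aim 2. For example, section C.5 reports a repeat correlation of 0.81 for flow-mediated dilation, on consecutive days in 20 healthy people. In the same formula that gives a partial r of only 0.012, 0.026 and 0.047 at c = 0.2, 0.3 and 0.4.

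Finally, any covariate list can be lengthened. Here, though, the protocol itself raises apnea as a concern, and the values belong to its own screening.

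**Conclusion.** The omission is real, and it leaves possible residual confounding in a non-randomised comparison. The documents cannot show that bias is present or how large it would be. Under the stated assumptions the effect on the dipping analysis is negligible at correlations of 0.2 and small at 0.3. It reaches a spurious r of about 0.07 and an error rate of about 11% only when both correlations are 0.4, and these figures precede adjustment for the other planned covariates. No size is claimed for Aim 2.

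A reader might infer a much larger problem by assuming that correlations of 0.3 on both sides survive all six planned covariates. That would give r = 0.3 × 0.3 = 0.09 and an error rate of 16.5%. It is a stronger assumption, and nothing in the documents supports it. The point is a cheap improvement.

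**What to change.** - Add continuous baseline BMI to the prespecified covariates of the Aim 1 and Aim 2 models, including the six-month mixed models. The text supplied describes no height or weight procedure; that BMI is collected is inferred from the BMI exclusion and the STOP-BANG item, so the plan should confirm it.
- Report a sensitivity model that also adds the screening STOP-BANG score. State that the score overlaps with age, gender, BMI and blood pressure and so carries limited apnea-specific information.
- Treat any AHI-adjusted model as descriptive only. AHI exists only in a subset selected on suspicion of apnea.

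The cost is plan wording and one degree of freedom in the main models, two in the sensitivity model. For Aim 1, power at r = 0.25 goes from 0.7923 to 0.7889 and 0.7855 respectively. Settling this before analysis also avoids choosing covariates after the results are seen.

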#### ANALYSIS PLAN

Data will be entered into a secure Microsoft Access database. Entry to the database is limited to key personnel and is password protected at the point of the workstation and the application. Standard double-entry and data checking approaches will be performed for all measures.

General Analytic Approach: Descriptive statistics will be performed on all study variables. In order to mitigate potential bias due to transient improvements in either sleep or BP dipping, we will utilize a 6-wk run-in phase after which participants will have their sleep efficiency and BP dipping markers re-assessed to ensure stability. Although we do not anticipate significant variation in either sleep or BP parameters during this pre-treatment phase, we will exclude participants who no longer meet inclusion criteria following the 6-wk run-in period. This practice has been shown to result in an increased magnitude of treatment improvements and therefore may improve the statistical power and potential precision of the proposed analyses. Markers of sleep efficiency and BP dipping collected after our run-in phase will therefore be used as our baseline assessment measures.

Regression-based analytic approaches will be used to examine associations between improved sleep efficiency, ABP indices, and mechanisms of CVD risk. In order to minimize potential confounding of treatment improvements due to either misdiagnosis or transient fluctuations in sleep, we will use assessments collected after the run-in period as our baseline time point. For our 6-week outcomes, improvements in sleep efficiency and ABP will be examined using simple regression analyses as detailed below. In contrast, our 6-month outcomes will be examined using repeated measures mixed models with an unstructured covariance matrix, using both 6-week and 6-month levels of the outcome modeled jointly. Incorporating both outcomes into a unified, mixed modeling approach will allow us to examine improvements in sleep as they associate with trajectories of BP dipping improvements and also allows for more robust handling of missing data.

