Power and Sample Size Considerations: Our power estimates were derived from prior data assessing sleep efficiency and nighttime BP dipping among individuals with HTN using the following assumptions: an initial sample size of 150 individuals, attrition of 15%, an alpha of 0.05, and a correlation of  $r = 0.30$  between sleep efficiency and BP dipping. Using these assumptions, we will have 80% power to detect correlations of  $r \geq 0.25$  between improvements in sleep efficiency and BP outcomes, suggesting that we will have adequate power to test the proposed hypotheses. In a more conservative scenario for comparing the worst 1/3 of the sample in terms of sleep efficiency change to the best 1/3, and assuming 50 participants in each group, there is 0.85 power at the two-sided 0.05 significance level for the detectable effect size  $\theta = 0.6$  via the following equation:  $(n \text{ per group}) = 50 = 2 * (((1.96 + 1.04) / 0.6) ** 2)$ . In the present proposal, this corresponds to a difference of 2.2% in SBP dipping between high and low sleep efficiency groups.

Exploratory Analyses of Effect Modification: In addition to our formal analyses, we will conduct exploratory analyses of effect modification, which will be interpreted as hypothesis generating. Candidate markers for effect modification will include background and clinical characteristics, such as race, gender, baseline insomnia severity, baseline anxiety, and the presence of elevated depressive symptoms ( $BDI > 14$ ). Specifically, we will examine the interaction terms between these candidate moderators, changes in sleep efficiency and mechanisms of CVD risk using the same general linear modeling approach noted for Hypothesis 2.

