## D.2. METHODOLOGICAL ISSUES

For this mechanistic study, we considered several alternative designs, including a cross-sectional observational study and a two-group randomized design. A cross-sectional design was rejected because differences in CVD risk factors between patients with poor sleep quality and good sleep quality could be due to other factors besides their sleep. However, because the study objective was mechanistic, with the (favorable) manipulation of sleep quality of primary interest as the independent variable, and

because CBT-I has emerged as the gold standard for treating insomnia, we could not uphold the principle of equipoise in a design that randomized participants to an intervention that would likely be markedly less effective in treating their insomnia (e.g., sleep hygiene, no treatment, wait-list control). Moreover, the study objective is not to ascertain the efficacy of CBT-I, so a randomized design and comparison group is not required. Indeed, with the efficacy of CBT-I at approximately 60%, the more ethically defensible design was considered to be that all participants should receive the CBT-I intervention, with a time-equivalent run-in phase serving as a within-participant control phase to help establish that more marked alterations in sleep quality (60%) should be attributed to the CBT-I intervention, with an estimated 40% showing minimal to clinically insignificant changes.

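### The Aim 1 model adjusts for one post-run-in sleep efficiency value and one post-run-in dipping value; if both carry error, stable differences between people can push the slope upward and the within-person test above 5%

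*Combined protocol and SAP*

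**What the plan says.** Under Analysis Plan, Aim 1, post-treatment dipping is regressed on improvement in sleep quality, "controlling for age, gender, race, baseline sleep efficiency, baseline mean 24-hour BP, and pretreatment BP dipping, with post-treatment BP dipping as the criterion". The test level is fixed in advance at P = .05.

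The General Analytic Approach fixes which pre-treatment values count: "Markers of sleep efficiency and BP dipping collected after our run-in phase will therefore be used as our baseline assessment measures". Design & Procedures also schedules an assessment before the run-in. The analysis plan uses it only to check stability.

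Each dipping value comes from one 24-hour ambulatory record (section C.5). SE is an average over several days of actigraphy (section C.4). No reliability is given for either.

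Aim 1 asks whether changes in sleep quality modify the circadian BP profile, which is a within-person question. Section D.2 rejects a cross-sectional design because "differences in CVD risk factors between patients with poor sleep quality and good sleep quality could be due to other factors besides their sleep".

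**The concern.** With baseline SE in the model, the coefficient on SE change is algebraically the coefficient on post-treatment SE. Post-treatment SE reflects the response to CBT-I, but it also says something about how the person usually sleeps. If baseline SE is noisy, it does not absorb all of that. If pretreatment dipping is noisy too, it does not absorb all of the person's usual dipping. Any stable correlation between usual sleep and usual dipping then passes through the two gaps and appears as a positive slope.

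Nothing has to change during the trial for this to happen, so it is distinct from time-varying confounding. The bias runs in the direction of Hypothesis 1. In a single-arm study the mechanistic reading rests largely on this slope, and part of the between-person confounding that section D.2 set out to avoid can return through it.

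**Working it through.** **Inputs from the plan** (Power and Sample Size Considerations). The assumptions are "an initial sample size of 150 individuals, attrition of 15%, an alpha of 0.05" and r = 0.30 between SE and dipping. Analysed n is 150 × 0.85 = 127.5, taken as 127. The test is taken as two-sided, as stated for the tertile comparison.

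**The plan's own figures reproduce.** For r = 0.25: atanh(0.25) × √(127 − 3) = 0.2554 × 11.136 = 2.844, and Φ(2.844 − 1.96) = Φ(0.884) = 81%, against the stated 80%. For the tertiles: 2 × ((1.96 + 1.04)/0.6)² = 2 × 25 = 50 per group, as stated.

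**Assumptions not in the plan.**
- SE reliability λs is 0.6–0.9 and dipping reliability λd is 0.4–0.7.
- Treatment-induced SE change has an SD of 0.5–1.0 baseline SDs (variance v = 0.25–1.0).
- r = 0.30 is the observed cross-sectional correlation c and is wholly between-person.
- Errors are independent between visits, and SE response is unrelated to dipping.
- There is no within-person effect.
- Age, gender, race and 24-hour BP are treated as unrelated covariates.

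**Closed form.** Scale baseline SE and dipping to variance 1. Given baseline SE and pretreatment dipping:

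- residual covariance of post-treatment SE and dipping = c(1 − λs)(1 − λd)/(1 − c²)
- residual variance of SE = 1 + v − (λs² − 2c²λs + c²)/(1 − c²)
- residual variance of dipping = 1 − (λd² − 2c²λd + c²)/(1 − c²)

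The covariance is zero if either λs = 1 or λd = 1. Error in both measures is therefore necessary.

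**Central case** (λs 0.7, λd 0.5, v 0.25). Covariance = 0.30 × 0.3 × 0.5/0.91 = 0.0495. Variances = 1.25 − 0.454/0.91 = 0.751 and 1 − 0.25/0.91 = 0.725. Partial r = 0.0495/√(0.751 × 0.725) = 0.067. With six conditioning variables, z = 0.067 × √(127 − 6 − 3) = 0.067 × 10.86 = 0.73. Rejection = Φ(0.73 − 1.96) + Φ(−0.73 − 1.96) = 11.3%. Simulation gives 10.6%.

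**Range at r = 0.30** (closed form, change SD 0.5–1.0, λd 0.4–0.7):

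| SE reliability | Rejection |
|---|---|
| 0.9 | 5.2–6.5% |
| 0.8 | 5.8–9.4% |
| 0.7 | 6.6–13.2% |
| 0.6 | 7.6–17.7% |

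At r = 0.20 the same grid gives 5.1–9.8%. If true SE change correlates −0.5 with baseline SE, the 0.7/0.5 case gives 5.7–8.9%.

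**Using both pre-treatment records, central case.** The means of two records have variances Vs = 0.7 + 0.3/2 = 0.85 and Vd = 0.5 + 0.5/2 = 0.75. The covariance becomes c(Vs − λs)(Vd − λd)/(VsVd − c²) = 0.30 × 0.15 × 0.25/0.5475 = 0.0205. The residual variances become 1.25 − 0.318/0.5475 = 0.669 and 1 − 0.19/0.5475 = 0.653. Partial r = 0.0205/√(0.669 × 0.653) = 0.031, so z = 0.34 and rejection is about 6.3%. In simulation, entering the earlier values as extra covariates took 10.6% to 6.2%, with a slope standard error of 0.091 against 0.090. In the harshest simulated case (0.6/0.4, SD 0.5), averaging took 18.6% to 8.8%.

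**Change in dipping on change in SE.** In simulations under the error model above this rejected 4.5–5.6%. Its standard error was about 0.104 against 0.090 (0.104/0.090 = 1.16), or 16–17% wider. If SE response correlates −0.2 to −0.3 with the recorded pre-treatment dip, it rejected 12.7–23.1%.

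**The case against.** A reader might infer that the single dipping record is the culprit and that the plan's test rejects 6–18% of the time as a matter of fact. The documents support neither. Dipping noise alone causes no leak, and SE, averaged over several days, may well be the more reliable measure. The range rests on reliabilities and a change SD that the plan does not give. Section C.5 also calls one successful ambulatory record adequate, although that is not a reliability coefficient for dipping.

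The upper end needs strong inputs. Holding the observed r at 0.30 implies a stable correlation of 0.30/√(0.7 × 0.5) = 0.51 in the central case and 0.30/√(0.6 × 0.4) = 0.61 in the harshest, all of it non-causal. The plan says only "Our power estimates were derived from prior data assessing sleep efficiency and nighttime BP dipping among individuals with HTN". It does not say that r is cross-sectional or stable.

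A reader might also infer that the model brings back the whole of the confounding rejected in section D.2. It does not. Spurious partial correlations of about 0.03–0.09 against 0.30 mean that roughly 70–90% is removed (1 − 0.09/0.30 and 1 − 0.03/0.30), and the residue lies well below the r = 0.25 the study is powered for.

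Finally, Hypothesis 1 is worded as an association, and the error rate for that association is intact. All of this stands, and it limits the size. It does not remove the upward direction of the bias for the within-person reading that Aim 1 asks for, nor the fact that data which would reduce it go unused.

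**Conclusion.** The point holds in conditional form. When baseline SE and baseline dipping both carry error, and usual sleep tracks usual dipping between people, the primary slope is biased upward and the test of the within-person claim can exceed 5%. At r = 0.30, wholly between-person, the assumed reliabilities put rejection at about 5–18%; with SE reliability of 0.8–0.9 it is about 5–9% and may be indistinguishable from nominal. At r = 0.20 it is about 5–10%. If either measure is error-free or r = 0, it is 5%. Real correlations with the other covariates could move these figures, and the 6-month mixed model was not simulated.

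It is tempting to conclude that a change-score model should replace the planned one or settle the interpretation. That does not follow, because the change-score model fails in its own way when SE response tracks the recorded dip.

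**What to change.** 1. In the Aim 1 model and its 6-month counterpart, add SE and SBP dipping from the pre-run-in visit as covariates. The post-run-in values remain the baseline from which improvement is measured. The mean of the two pre-treatment records is an alternative; SE improvement should then be measured from the same mean. Cost: SAP wording, two more covariates, and almost no precision (0.091 against 0.090).

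2. Prespecify a sensitivity analysis that regresses change in dipping (post-CBT-I minus post-run-in) on change in SE, adjusted for age, gender, race and baseline SE, but not for pretreatment dipping or baseline 24-hour BP. State its two limits: a standard error 16–17% wider, and bias if SE response tracks the recorded pre-treatment dip. With a 17% wider standard error, power at r = 0.25 would fall from 81% to about Φ(2.844/1.17 − 1.96) = Φ(0.47) = 68%, so it should not be the primary test.

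3. State how disagreement will be read: the primary slope is then reported as an association that may partly be between-person. A non-significant change-score result alone should not overturn it.

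4. Report the correlation between the pre-run-in and post-run-in values of SE and of dipping, so that readers can place the trial within the range above. This needs no new data.
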